### 2.2 Study Population

The target population is HIV positive patients receiving effective treatment with ART and at low risk for AIDS defining complications. For these participants, non-AIDS defining long-term complications (e.g., CVD and cancer) dominate the spectrum of morbidity and mortality. We will also focus on participants over age 50, as advanced age is

associated with inflammation, poor immune recovery, and also increased risk for long-term complications such as CVD and cancer. Any antiretroviral medications can be used. Detailed inclusion and exclusion criteria are listed below. There are no restrictions on the use of concurrent medications other than ARB or ACE-I, but participants with common diseases known to be pro-inflammatory will be excluded.

## 2.3 Eligibility Criteria

### Inclusion Criteria

- HIV infection (verified by previous positive antibody or detectable HIV RNA level)
- Age  $\geq 50$  years
- Receiving continuous ART for  $\geq 2$  years; regimen changes acceptable if  $>4$  weeks prior to screening when there is an ART class change (i.e., corresponding to either a deletion or addition of an ART class), or at anytime for an antiretroviral change that is within an ART class.
- HIV RNA level  $\leq 200$  copies/mL for  $\geq 1$  year (1 measure  $\geq 200$  allowed if also  $<500$  and preceded and followed by one or more undetectable values)
- Blood CD4+ T-cell count  $\leq 600$  cells/mm^3
- Systolic blood pressure  $\geq 110$  mmHg (mean value, if  $\geq 2$  measures obtained)
- Estimated GFR  $\geq 30$  mL/min/1.73m^2
- Do not anticipate starting (or stopping) statin or aspirin therapy during the study
- For women of child bearing potential, agrees to use a reliable form of birth control

### Exclusion Criteria

- Pregnancy or breast feeding
- A contra-indication to taking an ARB (e.g., cirrhosis, prior angioedema with ACE-I, or use of drug with potential drug-interaction [e.g., rifaximin])
- A clinical indication for ARB or ACEi therapy
- Current treatment with ARB or medication with overlapping mechanism (e.g., ACE-I or aldosterone antagonist)
- Treatment with immune-modulatory drugs within the past 6 months
- Hepatitis C treatments (e.g., interferon, ribavirin) within the past 6 months
- Serum potassium  $>5.0$  mmol/L within the past 3 months
- Grade 3/4 lab abnormality (from BMP, CBC or liver function panel)
- Invasive cancer in the prior year or receiving cancer treatment (not including carcinoma-in-situ or basal cell cancer of the skin)
- Cirrhosis or end-stage liver disease
- Rheumatologic or chronic inflammatory disease (e.g., systemic lupus erythematosus, psoriasis, rheumatoid arthritis, vasculitis, sarcoidosis, Crohn's disease)
- Assessment by the clinical investigator that enrollment into the study could entail excess risk to the participant, beyond what is intended or expected.
- BMI  $>40$ mg/kg for participants co-enrolled into the LN biopsy substudy.

**NOTE:** For participants consented to co-enroll into the LN biopsy substudy, the following approach based on BMI at screening visit will be applied:

- i. BMI  $\leq$ 30: participants can be co-enrolled into LN substudy. A LN assessment should be done upon consent (by MD, NP, or RN) to determine if the participant has palpable LN in the inguinal region. Findings will be documented on the LN Biopsy Referral Form.
- ii. BMI 30-40: participants must have documentation of palpable LN in the inguinal region at the screening visit.
- iii. BMI  $>$ 40: participants are not eligible for LN biopsy substudy.

## 2.4 Study Medication Intervention

At baseline, participants will start losartan or matching placebo at 50mg daily. At 2 weeks, side effects and blood chemistries (BMP) will be assessed. The dose of losartan/placebo will increase to 100mg daily at the week 2 assessment if no toxicities or side effects are present that are attributable to study medication (see section 3.2 below for specific study drug dose modification criteria). A similar repeat assessment will then be performed at month 1 to verify that the 100mg dose is tolerated.

### Randomization and Blinding

Eligible participants who consent to study procedures will be randomized 1:1 to receive losartan or matching placebo, with stratification by clinical site and by whether the participant consents to undergo a LN biopsy. Treatment assignments will be generated using a permuted block randomization scheme. Sites will use a secure, on-line program to obtain treatment assignments. The program will also verify eligibility and the existence of key baseline data. Treatment assignments will be verified and recorded in a dataset blinded to view by site staff.

A bottle ID number (BID) unique to each bottle will be assigned to participants, and used by study staff to obtain the correct blinded study drug. Sites will not have access to the treatment assignment linked to each bottle number, and bottle numbers will not be assigned in sequence.

Blinding will occur at 3 levels: 1) treatment assignment will be blinded, 2) interim data summaries will be blinded to all but the unblinded statistician and 3) core lab staff will be blinded to treatment group. In the rare event that the blind must be broken, every effort will be made to minimize the extent of the unblinding (for staff and participants) and an assessment of blinding will occur at the end of the study.

### Study Drug Production and Distribution

Active losartan 50mg tablets and matching placebo will be provided and distributed by Merck Pharmaceuticals. From baseline to 1-month visit, participants will take one 50mg tablet daily. When/if the study drug dose is increased to 100mg, participants will take 2x 50mg tabs once daily (for 100mg). Study drugs will be provided in 100 count bottles. One bottle will be dispensed at baseline, and one additional bottle at the 1-month visit. Following this, 2 bottles will be dispensed at all subsequent visits (months 3, 6, and 9). Sites will order study drug from the DCC, which will communicate with Merck to ship

drug to sites. Merck will provide the DCC with the key linking the BID (unique to each bottle) with whether the contents are active losartan or matching placebo. The DCC will then instruct sites which bottle(s) to dispense to patients based on the BID.

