## 2 METHODOLOGY

### 2.1 Trial Design

The potential benefits of losartan (100mg daily) will be studied among HIV positive individuals over age 50 years whose CD4 counts remain  $\leq 600$  cells/mm^3. Participants (n=120, 60 per group) will be randomized to receive losartan or matching placebo daily. After randomization, participants will start losartan (or placebo) at a dose of 50mg once daily, increasing to 100mg once daily at the 2-week study visit pending results of a week 2 toxicity lab evaluation (see 2.4 below for criteria). Following month 1, participants will return for follow-up study visit procedures at months 3, 6, 9, and 12. A lymph node biopsy will also be performed at baseline and month 12 from a subset of participants (n $\geq$ 30).

Changes from baseline in measures of inflammation, immune activation, immune recovery and fibrosis within lymphatic tissues will be studied. The primary outcome will be the average of IL-6 levels over 12 months, and the main secondary outcome will be change in CD4 count in blood over 12 months.

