## 2.6 Study Visit Schedule

Participants will be screened and, if eligibility criteria are met, will be randomized at the baseline visit to start active study drug or matched placebo (blinded). Randomization must occur within 90 days of all screening labs. *NOTE: the 90-day screening to randomization window applies to all participants, both those co-enrolled into the LN biopsy substudy and those not co-enrolled.*

Baseline laboratory evaluation must occur within 30 days of randomization. For participants enrolled in the LN biopsy substudy, baseline labs cannot be drawn within the 7 days following the biopsy procedure. A LN biopsy specimen must be obtained prior to randomizing the participant into the LN substudy. If a biopsy procedure is attempted but a LN specimen is not obtained at baseline, the participant will still be eligible to be randomized into the main study (but not the LN substudy). *NOTE: the biopsy procedure may occur after the baseline labs are obtained but still prior to randomization.*

After screening and baseline visits, participants will start losartan 50mg daily (or placebo) and return for a lab draw to assess toxicity (BMP only) at week 2. At the week 2 visit (after toxicity lab results return), participants will increase to losartan 100mg daily (or placebo) if they meet criteria based on results from the 2-week assessment (see section 2.4 above). Subsequent study visit procedures will occur in the context of visits at months 1, 3, 6, 9, and 12. For participants enrolled in the LN biopsy substudy, month 12 visit labs cannot be drawn within the 7 days following the month 12 biopsy procedure (*NOTE: the biopsy procedure may occur after the month 12 labs are obtained*). Participant should continue to take study medication until all study visits are completed; for participants enrolled in the LN biopsy substudy this includes BOTH the month 12 biopsy as well as the month 12 labs.

The target visit window for each study visit is guided by anticipated study drug quantity that the participant will have at the time. For week 2 and month 1, this corresponds to a 14-day target window (or +/- 7 days). Corresponding target windows for month 3, 6, 9, and 12 study visits are 32 days (or +/- 16 days).

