### **3.2 Study Drug Dose Modification**

At baseline, participants will start losartan or matching placebo at 50mg daily. At 2 weeks, side effects and blood chemistries (basic metabolic panel [BMP]) will be assessed. The dose of losartan/placebo will increase to 100mg daily at this week 2 visit (i.e., once lab results return) if all of the following criteria are met:

- a) Systolic blood pressure (BP) ≥90 mmHg

- b) Potassium  $\leq 5.0$  mmol/L
- c) eGFR  $\geq 30$  mL/min/1.73m^2
- d) Lack of a grade  $\geq 3$  side effect since the last evaluation deemed possibly/probably related to the study drug.
- e) Lack of significant side effects deemed related to study drug (e.g., lightheaded upon standing)
- f) Lack of other concerns to increase study drug dosing, as determined by site investigator

If participants are increased to 100mg dose at the week 2 visit and continue to tolerate this dose at the month 1 visit, they will be contacted by phone to verify tolerability 2-4 weeks following the month 1 visit. Participants may be evaluated by clinical labs and/or have side effects assessed at any point during the study, per the discretion of the site investigator. If participants are increased to 100mg daily (or matching placebo) they will maintain this dose for the duration of the 12-month study unless new side effects or adverse events necessitate re-evaluation (see below criteria).

If participants do NOT increase dose to 100mg daily at the week 2 visit (e.g., if symptomatic or if systolic BP is not  $\geq 90$  mmHg), the criteria for dose escalation may be reassessed at the 1-month visit. If participants do not meet criteria for dose increase (from 50mg to 100mg daily) after the 1-month visit, they will be maintained on 50mg dose until the month 3 visit, at which time the dose may be increased to 100mg daily if the five criteria above are met (a-e). At any point when participants have dose increased from 50mg to 100mg, they will be contacted by phone within 2 weeks to assess side effects and have clinical labs drawn to assess toxicity; a full study visit for side effect and adverse event documentation can occur at any point, per the discretion of the site investigator.

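### The drug distribution paragraph keeps participants on one 50 mg tablet daily to month 1, whereas sections 2.1, 2.4, 2.6 and 3.2 raise those who qualify to 100 mg at week 2

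*Combined protocol and SAP*

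**What the plan says.** The paragraph on Study Drug Production and Distribution, a subsection of 2.4, gives the tablet instruction "From baseline to 1-month visit, participants will take one 50mg tablet daily". The sentence after it says that 100 mg is taken as two 50 mg tablets, but does not say when that dose begins. On supply: "One bottle will be dispensed at baseline, and one additional bottle at the 1-month visit", each bottle holding 100 tablets.

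The other dosing text is consistent and different:

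- Section 2.1 has participants start at 50 mg, "increasing to 100mg once daily at the 2-week study visit pending results of a week 2 toxicity lab evaluation".
- Section 2.4, main text: "The dose of losartan/placebo will increase to 100mg daily at the week 2 assessment", provided no attributable toxicity is present. It adds: "A similar repeat assessment will then be performed at month 1 to verify that the 100mg dose is tolerated".
- Section 2.6: "At the week 2 visit (after toxicity lab results return), participants will increase to losartan 100mg daily (or placebo) if they meet criteria".
- Section 3.2 lists six criteria (a to f) for the week 2 increase. It then plans a follow-up telephone call, with the condition "If participants are increased to 100mg dose at the week 2 visit and continue to tolerate this dose at the month 1 visit". For participants not increased at week 2, it allows the criteria to be looked at again at month 1.

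**The concern.** For a participant who meets the criteria at week 2, the two instructions cannot both be followed. Between week 2 and month 1 the distribution paragraph means one tablet a day, and the other sections mean two. This is an operative dosing instruction, and a site pharmacist or the author of a participant leaflet could reasonably take tablet directions from the paragraph that deals with tablets and bottles.

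Two things are at stake. The first is exposure in the second half of month 1, just before the first of the five post-baseline IL-6 samples (months 1, 3, 6, 9 and 12 in section 6). The second is the purpose of the month 1 assessment: if participants are still on 50 mg, it cannot show whether 100 mg is tolerated.

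**Working it through.** **Step 1. Which text is the outlier?** The documents give no figure to reproduce here, so the texts are set side by side.

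| Place | Dose from week 2 to month 1 if criteria are met |
|---|---|
| 2.4, Study Drug Production and Distribution | one tablet (50 mg) |
| 2.1 Trial Design | 100 mg |
| 2.4, main text | 100 mg, checked at month 1 |
| 2.6 Study Visit Schedule | 100 mg |
| 3.2 Study Drug Dose Modification | 100 mg, tolerance reviewed at month 1 |

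The month 1 checks in 2.4 and 3.2 make sense only if 100 mg has already begun. The distribution sentence is correct for one group: participants not increased at week 2.

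**Step 2. Supply as a cross-check.** Section 2.6 says that visit windows follow the drug quantity a participant is expected to hold. Two bottles, 200 tablets, are dispensed before month 3. If the increase is on day e, the tablets last to day e + (200 − e)/2.

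- e = 14: 14 + 186/2 = day 107.
- e = 30: 30 + 170/2 = day 115.

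Taking month 3 as day 91 (an assumption), the slack is 107 − 91 = 16 days or 115 − 91 = 24 days. The stated target window for month 3 is ±16 days, which fits a week 2 increase. The exact match depends on day 91; at day 90 or 92 the slack would be 17 or 15 days. This supports Step 1 but is not needed for it.

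**Step 3. Size at target dates.** The protocol does not define the length of a month, so M = 28 and M = 30 days are assumed. Let d be the days on one tablet before the increase (target d = 14).

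- Days at half the intended dose = M − d: 28 − 14 = 14, or 30 − 14 = 16.
- Tablets by month 1 under the distribution paragraph = M: 28 or 30.
- Tablets by month 1 under the week 2 schedule = d + 2(M − d) = 2M − d: 56 − 14 = 42, or 60 − 14 = 46.
- Cumulative dose at 50 mg per tablet: 1,400 against 2,100 mg, or 1,500 against 2,300 mg.

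The increase waits for laboratory results, so the true number of days affected would be slightly smaller.

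**Step 4. Effect of the visit windows.** Section 2.6 gives both week 2 and month 1 a window of ±7 days. Varying week 2 alone (d from 7 to 21), with month 1 on its target date, the week 2 schedule uses 49 down to 35 tablets (M = 28) or 53 down to 39 (M = 30). With both windows:

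- 28-day month: lowest 2 × 21 − 21 = 21, highest 2 × 35 − 7 = 63.
- 30-day month: lowest 2 × 23 − 21 = 25, highest 2 × 37 − 7 = 67.

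**Step 5. Would supply reveal the error?** No. At target dates the 100-tablet baseline bottle leaves 72 or 58 tablets (M = 28), or 70 or 54 (M = 30). Even the highest count in Step 4, 67, is below 100.

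**The case against.** The strongest reply is that the governing text already settles the matter. The main text of 2.4 precedes the distribution paragraph, sets the week 2 increase and refers the reader to section 3.2, which is detailed and clear. The week 2 visit exists largely to support that increase. To follow the distribution sentence literally, a site would have to disregard four other statements. This largely stands, and it is why the point is minor. It does not make the sentence correct. The sentence that follows it does not rescue it either: it gives the number of tablets at 100 mg but no date, and read in order it seems to describe what happens after month 1.

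A reader might infer more, in two ways.

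- **Adherence.** Setting the two tablet counts against each other, full adherence to the distribution sentence would score 28/42 = 67% or 30/46 = 65% against the week 2 schedule. Full adherence to that schedule would score 42/28 = 150% or 46/30 = 153% against the distribution sentence. It is tempting to conclude that the adherence outcome, or the per-protocol and compliance-adjusted analyses, would be distorted. The documents do not support that. Section 3.3 names self-report and pill count without a denominator, section 6 gives no formula, and the case report form and implementation manual are not available. The percentages arise only under an assumed rule.
- **Primary result.** One might infer a diluted treatment effect. The documents do not show how many participants, if any, would be underdosed, or what two weeks at 50 mg would do to IL-6. The primary analysis is by intention to treat over five visits. No loss of power, change in type I error or bias is shown, and no gap in safety follow-up.

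**Conclusion.** The sentence is wrong as written, and the matter is minor. It contradicts sections 2.1, 2.4 (main text), 2.6 and 3.2 for every participant who qualifies for the week 2 increase. That conclusion rests on the text alone and needs no assumption. Its size does need one: with month 1 at day 28 or 30 and visits on target, literal compliance means about 14 to 16 days at half the intended dose. The practical risk is limited to instructions drawn from the distribution paragraph without reference to section 3.2.

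**What to change.** Replace the sentence in Study Drug Production and Distribution with: *One 50mg tablet once daily from baseline until the dose is increased (planned at the week 2 visit once labs return, if section 3.2 criteria are met), then two 50mg tablets once daily.* This also covers participants increased later, because it ties the tablet count to the increase and not to a visit.

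The cost is one sentence, plus a check that any dispensing label or participant instruction says the same. No visit, blood draw or extra drug is needed. How the pill-count denominator is defined is a separate matter: increase dates will vary however this sentence reads, so no change to it follows from this contradiction.

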### **Risks Associated with Study Drug**

Losartan is approved by the FDA and used to treat high blood pressure. Possible side effects of losartan include dizziness, lightheadedness, headache, fatigue, cough, upset stomach, vomiting, diarrhea, sore throat, fever, sweating, fast heart rate, chest pain, weakness, anemia, allergic reaction and kidney damage. In clinical studies, most of these side effects were no more common than what was experienced with placebo medication. Participants will undergo a side effect assessment at each visit (see case report form and protocol implementation manual for 'symptom check list').

Losartan should not be used during pregnancy. If a developing fetus is exposed to losartan, injury or even death may result. For this reason, pregnancy is an exclusion criterion and any pre-menopausal women of child bearing potential must be willing to use birth control during the study.

## **2.5 Outcomes**

### **Primary Outcome**

- IL-6 plasma levels: change from baseline over 12 months

### **Main Secondary Outcome**

- CD4+ T-cell count in blood: change from baseline over 12 months

### **Additional Secondary Outcomes**

- Adherence
- Tolerability and side effects
- Monocyte activation immune-phenotyping (e.g., CD14+/CD16+)
- Systemic inflammatory biomarkers (e.g., sCD14, sCD163, TNF- $\alpha$ , sTNFr-1, IL-6r, high sensitivity C-reactive protein)
- Coagulation activity (e.g., D-dimer levels)
- T-cell activation and senescence phenotypes in blood
- Recovery of CD4+ T-cell subsets (e.g., naïve) in blood
- HIV-specific T-cell responses
- Plasma biomarkers of fibrosis (e.g., hyaluronic acid)
- Lymphatic Tissue fibrosis (LN biopsy substudy)
- Lymphatic Tissue cellular immune activation (LN biopsy substudy)
- Lymphatic Tissue T-cell homeostasis (LN biopsy substudy)
- Frailty assessment (including 5 components: unintentional weight loss, physical inactivity, exhaustion, weak grip strength and slow walk)

## 2.6 Study Visit Schedule

Participants will be screened and, if eligibility criteria are met, will be randomized at the baseline visit to start active study drug or matched placebo (blinded). Randomization must occur within 90 days of all screening labs. *NOTE: the 90-day screening to randomization window applies to all participants, both those co-enrolled into the LN biopsy substudy and those not co-enrolled.*

Baseline laboratory evaluation must occur within 30 days of randomization. For participants enrolled in the LN biopsy substudy, baseline labs cannot be drawn within the 7 days following the biopsy procedure. A LN biopsy specimen must be obtained prior to randomizing the participant into the LN substudy. If a biopsy procedure is attempted but a LN specimen is not obtained at baseline, the participant will still be eligible to be randomized into the main study (but not the LN substudy). *NOTE: the biopsy procedure may occur after the baseline labs are obtained but still prior to randomization.*

After screening and baseline visits, participants will start losartan 50mg daily (or placebo) and return for a lab draw to assess toxicity (BMP only) at week 2. At the week 2 visit (after toxicity lab results return), participants will increase to losartan 100mg daily (or placebo) if they meet criteria based on results from the 2-week assessment (see section 2.4 above). Subsequent study visit procedures will occur in the context of visits at months 1, 3, 6, 9, and 12. For participants enrolled in the LN biopsy substudy, month 12 visit labs cannot be drawn within the 7 days following the month 12 biopsy procedure (*NOTE: the biopsy procedure may occur after the month 12 labs are obtained*). Participant should continue to take study medication until all study visits are completed; for participants enrolled in the LN biopsy substudy this includes BOTH the month 12 biopsy as well as the month 12 labs.

The target visit window for each study visit is guided by anticipated study drug quantity that the participant will have at the time. For week 2 and month 1, this corresponds to a 14-day target window (or +/- 7 days). Corresponding target windows for month 3, 6, 9, and 12 study visits are 32 days (or +/- 16 days).

*NOTE: the 'actual' visit window for months 3, 6, 9, and 12 will be +/- 42 days (i.e., no gaps between visits where participants would not be in a visit window), but if >16days additional study drug should be dispensed to the participant—consistent with making every effort to capture study visit data while keeping participants on study drug.*

The visit schedule is outlined in the table below. Patients will be fasting for all blood draws (except screening).

Toxicity labs and a clinical assessment will be ascertained as part of follow-up study visits. If clinical labs (e.g., HIV RNA level, CD4 count, BMP, hepatic panel, and CBC) are available as part of routine clinical monitoring during the study visit window, these results may be used in place of repeating clinic labs at the study visit. If new symptoms develop that may be related to study medications, the site study investigator is to be

notified within 24 hours and a clinical determination is to be made whether additional toxicity labs and/or adherence requires assessing.

